Prior to the starting the study in subjects with FAO disorders, individual study procedures such as the muscle and fat biopsies, the HEC and/or the MRS may be performed to practice the procedures and perfect them in up to 3 healthy volunteers. These control subjects may not specifically match data from FAO disorders. A separate consent form has been developed to consent these subjects.

Exclusion Criteria: Control subjects may not be participating in another study that alters their macronutrient intake such as low carbohydrate diet. All subjects will be screened for anemia prior to study participation. Female subjects of childbearing potential will be screened for pregnancy. Anemic (Hgb < 10 g/dl) or

pregnant subjects will be excluded from the study. Subjects regularly taking medications that strongly affect bleeding, bruising, or platelets such as Coumadin, Plavix, Aggrenox, Ticlid, Agrylin, Xagrid, Aricept, Namenda, Exelon, Razadyne or aspirin will be excluded from the study. Subjects may not have diabetes or be on medications to treat diabetes. Control subjects may not have a history of an endocrine disorder such as thyroid disease, renal disease or cardiovascular disease.

Inclusion of Children, Women and Minorities: All participants will be adults able to provide informed consent. We believe the complex full-day testing schedule planned for Day 2 of each inpatient admission, including two biopsies, is best conducted in the adult population. Both genders will be included in this research project. FAO disorders appear to occur equally in males and females so we expect to include similar numbers of males and females. Women of child-bearing potential are included in this research. Pregnant woman will be excluded because the DEXA scan would increase risk to the fetus and pregnancy may affect insulin sensitivity. Recruitment should result in study demographics similar to that of the national disease demographics. Caucasians will comprise the majority of subjects in this study. To date, the majority of patients with fatty acid oxidation disorders have been of Caucasian ancestry. We will welcome subjects from other racial backgrounds but anticipate that more, if not all, subjects will be white.

III.

Study Design

This is a randomized cross-over study in which all participants will complete 2 inpatient admissions with a 4-month washout period in between visits (**Figure 9**).

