The following day, the clamp study will begin at approximately 6:00 AM and end at about 4:00 PM (Day 2; **Figure 11**). Indirect calorimetry to measure energy expenditure and respiratory quotient for estimation of fat oxidation will be performed in the last hour of the clamp. The order of the intralipid vs. glycerol/saline infusion during HEC will be randomly assigned. Subjects will rest overnight and consume a standardized breakfast the following day (Day 3) and be discharged to home. Subjects will return 4 months later and repeat the admission with the alternative clamp procedure. If accurate clamp results are not achieved at Visit 1 or 2, the subject may be asked to return for another study visit to repeat the clamp procedure, DEXA, indirect calorimetry and/or biopsies. During periods of hospital recommendations for decreased in-person contact, study visits will be postponed until study staff are notified of return to normal research visit operations.

¹H and ¹³C MRS Procedure: of the liver and muscle: will be performed as previously described(18, 30) prior to (-100 min) and following both clamp procedures. Each subject will complete 4 MRS measurements of liver and muscle lipid content (**Figure 11**). Image-guided, ¹H localized, MRS following high-resolution T-weighted spin-echo imaging will be performed on a Siemens 3T whole-body system. Radiofrequency surface coils will be used for region-of-interest (ROI) voxel localization and spectroscopy data acquisition. Depending on the schedule for the MRS instruments and to allow for more time for a meal before the testing, the MRS measurements may not be completed until approximately 5:30 PM.

MRI of the abdomen to quantify visceral and subcutaneous fat: Although not a primary outcome, these measures will be acquired using a Siemens 3T system as previously described (18, 30).

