Blood and tissue metabolites collected from subjects with a FAO disorder and controls during clamps with and without co-infusion of intralipid will be measured by the West Coast Metabolomics Center (UC Davis, see specific methods below). Activation and expression of the insulin-signaling cascade components IR, AKT, PKC- Θ , will be measured in muscle and WAT samples as described in detail below. Basal and insulin-stimulated glucose and FFA uptake into muscle and WAT explants from biopsies will be measured by the novel florescence technique described above. Changes in insulin signaling and tissue fatty acid and glucose uptake between the intra-lipid and glycerol infusions will be compared between CPT2, VLCAD, and LCHAD/TFP-deficient subjects, subjects with MCAD deficiency, and normal controls.

IV.

Study Procedures

Table 4. Schedule of Study Procedures

	Screening Visit (Local Subjects)	Prior to Admit	At Admit or on Day 1	Day 2	Day 3
Informed Consent/HIPAA Authorization	X	X			
Inclusion/Exclusion Assessment	X	X	X		
Demographics and Medical History	X	X			
CBC with platelets, INR, PTT			X		
Pregnancy Test (if applicable)			X		
Vital Signs and Weight	X		X	X	X
Height	X		X		
Physical Exam			X		
Standard FAO Low Fat Diet		X	X	X	X
Low Fat Diet Instruction	X	X			
3-Day Diet Diary		X			
DEXA Scan			X		
Intravenous (IV) Catheter Placement			X		
Indirect Calorimetry				X	
Magnetic Resonance Spectroscopy (MRS)				X	
Hyperinsulinemic-Euglycemic Clamp (Figure 11)				X	
Muscle Biopsy				X	
Fat Biopsy				X	
Discharge from CTRC					X

Laboratory Methods:

Lab Assays: Insulin by RIA, leptin and total and high-molecular-weight adiponectin by ELISA, and FFA levels by enzymatic colorimetric kit will be determined by the OHSU CTRC Laboratory Core.

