analysis of insulin signaling. *Insulin-stimulated FFA and glucose uptake in WAT explants* from umbilical biopsies will be performed as previously established for non-human primate tissue and as shown in our previous publications and in **Figure 8**.(96-98) *Glucose uptake in skeletal muscle biopsies* will be evaluated in samples treated alone or with 10 nM insulin for 30 min and then exposed to 50 μ M 2-NBD-glucose for an additional 30 min. Samples are then washed, fixed in 4% paraformaldehyde, washed in HBSS with 50 mM CoCl₂, and stored in HBSS with 25 mM CoCl₂ until analyzed by confocal microscopy. 2-NBD-glucose incorporation into individual fibers is quantified using image J. Mean fluorescence per fiber is determined using a randomly positioned circular region of interest of cross-sectional images. *Insulin signaling pathway expression and activation* will be analyzed by preparing total protein lysates in RIPA buffer after homogenization in a motor-driven glass-glass homogenizer for muscle and in X buffer for WAT. Lysates are then subjected to standard Western immunoblotting for phosphorylated (activated) IR, Akt, and (in muscle) PKC- Θ , followed by stripping and probing with pan-IR, Akt, and PKC- Θ antibodies to determine general expression levels and for normalization of phospho-antibody signals as previously described.(24, 25, 63) We acknowledge that insulin receptor substrates (IRS)-1 and 2 are important components of the insulin signaling pathway in fat and muscle and are involved in insulin resistance, but it is our experience that analysis of IRS-1/2 activation requires significant amounts of lysate and immunoprecipitation prior to Western immunoblotting, which we are unlikely to acquire from the biopsies that will be obtained. The proposed analysis of IR, Akt, and PKC- Θ should, however, provide sufficient data to ascertain the status of the insulin-signaling pathway in samples from the different treatment groups.

V.

Statistical Analysis:

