The primary analyses to compare disease groups with healthy controls will use mixed models with a random effect for matched pair to allow for correlation between the observations on the matched observations. In addition to the random pair effect, a disease effect (disease versus healthy), and a diagnostic group effect (CPT2, VLCAD, LCHAD/TFP, MCAD), we will also incorporate a fixed effect for the order of testing (interlipid infusion tested first or second). The hypotheses focus on the comparisons between diseased individuals and their matched controls with regard to the difference in outcomes under the two conditions (glycerol vs interlipid infusion). For these analyses, we will use the difference in a given outcome (e.g., Rd uptake) between infusion conditions as the dependent variable and compare these differences between diseased and matched controls, separately for the four diagnostic groups (CPT2, VLCAD, LCHAD/TFP, MCAD). Although we will conduct a formal test of interaction of disease (disease vs healthy) and diagnostic group, we are not powered for such a test and, hence, will focus on separate inferences for the four disease groups. Note that, as indicated in the hypotheses, we expect to find differences between the controls and the CPT2, VLCAD, and LCHAD/TFP subjects, but not between the controls and the MCAD subjects. For the latter comparison, our emphasis will be on estimating the magnitude of the mean differences via 95% confidence intervals rather than formal hypothesis testing. We will use a significance level of 0.05 for each outcome comparison, with no adjustment for multiple comparisons due to the limited sample sizes. We are unable to increase sample sizes due to the small study populations and budgetary constraints, so cannot power the study to take into account the multiple comparisons. However, we will present for each outcome, both unadjusted p-values as well as p-values adjusted for the two multiple comparisons (one for each disease group) using the Holm procedure.(38)

Power Considerations:

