In **Table 6**, we show the differences between groups in mean change that can be detected with 80% power at level 0.05 when the sample size per long-chain disorders is 20. For n=10 subjects, we have adequate power for detecting expected differences for GIR and PDK4 mRNA with modest correlation between repeated observations on the same subject and between matched pairs. For GIR, even with zero correlation, we would have about 97% power at level 0.05 to detect the expected difference in change between groups (31.5 vs 5.7) with n=10. For PDK4 mRNA, we could detect the expected difference in change (-0.62 vs -0.18) with 63% power if zero correlation and with 78% power if the correlation is 0.25 between and within n=10 matched patients.

Table 5: Glucose Infusion Rate (GIR), and PDK4 mRNA/actin in healthy controls and hypothesized mean differences in subjects.				
Outcome	Glycerol Infusion	Interlipid Infusion	H_a : mean Δ In Controls and MCAD	H_a : mean Δ In VLCAD and LCHAD/TFP
GIR ($\mu\text{mol}/\text{kg}/\text{min}$) (n=9)	57.2 ± 9.3	25.7 ± 7.8	31.5	5.7
PDK4 (mRNA/actin) (n=10)	0.18 ± 0.06	0.8 ± 0.38	-0.62	-0.18

Data are mean \pm standard deviation from Roden et al and Tsintzas et al. GIR = glucose infusion rate; PDK4 = pyruvate dehydrogenase kinase 4; H_a : mean Δ = hypothesized mean difference.

Table 6: Change between glycerol infusion and interlipid infusion that can be detected between control and the VLCAD, LCHAD/TFP and CPT2 groups with 80% power at level 0.05 with n=20 subjects long-chain FAO disorders.				
Outcome	Mean Δ (Glycerol – Intralipid) Controls	Correlation between observations on the same subjects	Correlation of Δ between matched controls and patients	Mean Detectable Δ (Glycerol – Intralipid)* LCHAD/TFP subjects
GIR	31.5	.25	.25	17.6
	31.5	.50	.25	20.0
	31.5	.50	.50	22.1
PDK4 mRNA	0.62	.25	.25	0.17
	0.62	.50	.25	0.19
	0.62	.50	.50	0.27

Δ = change; * Note that changes smaller than these can be detected with greater power as smaller changes are further from the changes expected in the control groups.

Timeline: Enrollment and clamp procedures will be completed in years 1, 2, and 3. Biopsy assays and insulin signaling measures will be completed real time with collection of the muscle and adipose samples during years 1-3. In year 4, we will batch analyze stored plasma, muscle, and adipose samples for metabolomics to control for run variation of the metabolomics methods, prepare manuscripts and present the results of the project.

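### Insulin-signalling blots are scheduled in real time although a subject's two biopsies are about 4 months apart, which adds avoidable run-to-run noise to the within-subject difference

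*Combined protocol and SAP*

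**What the plan says.** **Timing of the assays** (Statistical Analysis, Timeline): "Biopsy assays and insulin signaling measures will be completed real time with collection of the muscle and adipose samples during years 1-3". The next sentence treats metabolomics differently: in year 4, "we will batch analyze stored plasma, muscle, and adipose samples for metabolomics to control for run variation of the metabolomics methods".

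**Spacing of the two conditions** (Study Design): "all participants will complete 2 inpatient admissions with a 4-month washout period in between visits", and "Subjects will return 4 months later and repeat the admission with the alternative clamp procedure". The same section allows repeat visits and postponements, so some gaps may be longer.

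**What is analysed.** Study Design, on blood and tissue samples: "Changes in insulin signaling and tissue fatty acid and glucose uptake between the intra-lipid and glycerol infusions will be compared" across the diagnostic groups and controls. Statistical Analysis: "we will use the difference in a given outcome (e.g., Rd uptake) between infusion conditions as the dependent variable". The listed model terms are matched pair, disease, diagnostic group and order of testing. No run or batch term is listed.

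**The assay** (Study Procedures, Laboratory analysis of Tissue Biopsies): "Lysates are then subjected to standard Western immunoblotting for phosphorylated (activated) IR, Akt, and (in muscle) PKC- Θ". Blots are then stripped and reprobed with pan antibodies, and the phospho signal is normalised to the pan signal. The section mentions no reference lysate, no calibrator between blots and no rule placing a subject's two visits on one gel. For normalisation it refers to earlier publications.

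**Tissue handling** (Muscle and Adipose Biopsy Techniques): muscle pieces are frozen in liquid nitrogen at once. Fat is divided, with one portion used fresh for size and insulin-sensitivity measures and the other stored at -80 °C.

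**The concern.** The crossover makes each subject their own control, and the Aim 2 prediction for phosphorylated IR, Akt and PKC-theta is a prediction about change between infusions. If the two samples of a subject are blotted months apart, each change carries the error of two runs as well as the biological difference. The patient-control contrast carries up to four.

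Phospho/pan normalisation removes loading, total protein and anything else common to both probings of a membrane. It does not put two membranes on one scale, because error specific to one probing remains in the ratio.

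The plan accepts the principle for metabolomics, where samples are held and run together for exactly this reason. It gives no reason for treating the blots otherwise. With 8 pairs per diagnosis, and a sample size that the plan says cannot be increased, precision that can be kept at little cost is worth keeping. At stake is the ability to see whether the signalling response is lost or preserved in each diagnostic group.

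**Working it through.** **1. Does the text lead to separate runs?** The Timeline says the signalling measures are completed as samples are collected. Study Design puts a subject's two collections about 4 months apart. Together these imply separate runs. This is an inference, because gel layout is not described.

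**2. Algebra.** Work on a relative (log) scale. Let V be the variance of the within-subject intralipid-glycerol difference without run error, s the between-run SD, and q the correlation of differences within a matched pair.

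- Separate runs, within-subject difference: V + 2s². The ratio to V is 1 + 2s²/V.
- Four separate runs, patient-control contrast: 2V(1 − q) + 4s². The ratio is 1 + 2s²/[V(1 − q)], which is the same at q = 0 and larger at q > 0.
- Both visits on one gel: a multiplicative gel effect is common to both log values and drops out of their difference.

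**3. Size under stated assumptions.** The documents give neither V nor s for the blots, so both are assumed and varied. Each cell shows the variance ratio, then 8 divided by the unrounded ratio.

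| Between-run CV | Difference SD 30% (V = 0.09) | Difference SD 60% (V = 0.36) |
|---|---|---|
| 10% | 1.22; 6.5 | 1.06; 7.6 |
| 15% | 1.50; 5.3 | 1.13; 7.1 |
| 20% | 1.89; 4.2 | 1.22; 6.5 |
| 30% | 3.00; 2.7 | 1.50; 5.3 |

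Example: (0.09 + 2 × 0.20²)/0.09 = 0.17/0.09 = 1.89, and 8/1.89 = 4.2.

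The 60% column has a rough anchor. For PDK4 mRNA, the only tissue outcome with SDs in the plan (Table 5), the difference SD at zero correlation is √(0.06² + 0.38²) = 0.385. The mean change is 0.62, and 0.385/0.62 is about 62%.

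**4. Cross-check with the plan's own power method.** The plan gives no power figure for the blots. Its PDK4 figures (Power Considerations) are 63% at zero correlation and 78% with both correlations 0.25, for n = 10 pairs and an expected difference in change of 0.62 − 0.18 = 0.44. A paired t-test on the pair contrast, two-sided 0.05, reproduces them:

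- Zero correlation: SD = 0.3847 × √2 = 0.544. Power is 0.626.
- Both correlations 0.25: difference SD = √(0.148 − 2 × 0.25 × 0.06 × 0.38) = 0.3696, and contrast SD = 0.3696 × √(2 × 0.75) = 0.453. Power is 0.781.

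Now use PDK4 as a stand-in at the recruited size of 8 pairs, with both correlations 0.25. Add run error with SD equal to an assumed fraction f of the pooled per-measurement SD, √(0.148/2) = 0.272, in four separate runs:

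| f | Contrast variance ratio | Power, n = 8 |
|---|---|---|
| 0 | 1.00 | 0.657 |
| 0.1 | 1.01 | 0.650 |
| 0.25 | 1.09 | 0.620 |
| 0.5 | 1.36 | 0.528 |
| 1.0 | 2.45 | 0.330 |

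The loss is trivial when run error is small and large when it approaches the biological SD.

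**The case against.** The strongest reply is that separate runs are inferred. Real-time work in years 1-3 is set against a year-4 batch and could mean ongoing work during collection, not each visit blotted alone. Frozen muscle and stored fat would allow a subject's two visits to be paired within those years, and the cited normalisation methods, not reproduced in the plan, may cover handling between blots. This stands as a limit on certainty. It does not remove the point: the text as written leads to separate runs and states no safeguard.

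A second reply is that the damage may be slight. The blots are a mechanistic outcome, while power rests on glucose infusion rate and PDK4. The clamp, spectroscopy, explant uptake and metabolomics outcomes are untouched. With small run error the loss is a few percent. This stands too, and sets the weight of the point.

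A reader might go further and infer that run differences bias the comparison of infusions, or that an odd run could readily produce a false finding. The documents do not support that. Infusion order is randomised and fitted as a fixed effect, so an average shift from first to second visit is handled. The remaining random scatter also widens the standard error, so it chiefly costs power.

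A reader might also infer that the crossover's advantage is cancelled. It is not: between-subject variation is still removed, and precision is eroded by an unknown amount. Nor do the documents say when controls are studied relative to their matched patients, so four separate runs per pair is the upper case.

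**Conclusion.** The point holds as a matter of precision. As written, the schedule puts a subject's two signalling samples in different blot runs, and nothing stated in the laboratory methods or the model removes the resulting scatter from the analysed difference. The same paragraph removes it for metabolomics.

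The size cannot be fixed from the documents. The factor of about 1.06 to 3.0 rests on assumed values for both the difference SD and the between-run CV. Its upper end needs the smaller SD together with the largest CV, so it should not be read as the expected loss. The conclusion also rests on reading the real-time rule literally. It concerns the blots only; the fresh explant uptake assays cannot be batched. This is a worthwhile, inexpensive improvement to an Aim 2 outcome, and not a threat to the trial's main metabolic comparisons.

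**What to change.** Amend the Timeline sentence so that real-time work covers only the fresh explant glucose and FFA uptake assays. For the blots:

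- Hold frozen tissue or lysate until the subject's second visit, then run both visits on the same gel, with the matched control's two samples where available.
- Analyse the signalling outcome as the log ratio of the two infusions. A multiplicative gel effect cancels on that scale, whereas in a raw difference it only rescales the result.
- If samples must be run separately, put a common reference lysate on every blot, normalise to it, and say so in the laboratory methods.

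The cost is a change of wording and of laboratory schedule, with no extra samples or participant procedures. Signalling results arrive later, and first-visit samples spend at least 4 months in frozen storage. The documents give no data on the stability of phospho signals in storage. That favours blotting when each subject or pair is complete over holding everything to year 4. The reference-lysate option avoids the delay.

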saline/2.5% glycerol or 20% intralipid infusion of 1.5 ml/min will be started and continued until the 5-hour clamp has been completed and the muscle and fat biopsy have been performed. Blood glucose will be monitored every 5-10 min during the insulin infusion using a Hemocue Glucose 201(HemoCue America, Brea, CA), or an i-STAT analyzer (Abbott Point of Care Inc, Abbott Park, IL) and euglycemia will be maintained throughout the clamp by infusing 20% dextrose at a variable rate. To maintain a constant enrichment of [6,6-²H₂] glucose in blood during the clamp, [6,6-²H₂] glucose infusion will be continued throughout the clamp and at 2% enrichment in the 20% dextrose solution. Additional blood samples will be collected every 60 minutes for insulin, ketones, and FFA, and at the beginning and end of the clamp for ²H₂-glucose and metabolomics. Using the blood samples collected during the 30-minute period just preceding and at the end of the glucose clamp, glucose disposal rates (Rd) and basal endogenous glucose production (R_a) will be calculated according to the steady-state equations of Steele.(92) At the end of the 5 hour infusion and completion of the muscle and fat biopsies, the insulin and intralipid or glycerol/saline infusions will be stopped. After 10 minutes, the subject will be fed a low-fat meal. Blood glucose will continue to be monitored for an additional hour after the insulin infusion is stopped with adjustment to the glucose infusion as indicated to ensure subjects reestablish endogenous glucose regulation.

Rationale for HEC approach: Patients will undergo insulin sensitivity measurement using HECs along with determination of ectopic fat accumulation by ¹H magnetic resonance spectroscopy (MRS). If the defective mitochondrial function and "lipotoxicity" hypothesis is true, then insulin resistance should be common among patients with long-chain FAO disorders in whom FAO capacity is greatly reduced. However, insulin resistance and diabetes have not been previously reported in case reports of patients with CPT2, VLCAD, or LCHAD/TFP deficiency(35) and, in our preliminary data(30) (see also above), these patients have comparable levels of IMCL, IHL, and glucose tolerance to controls while consuming a low-fat diet.

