Muscle Biopsy Technique: Biopsies of the vastus lateralis muscle from study subjects will be obtained by percutaneous puncture using a Bergstrom side-cut needle(142) (144). Briefly, after local infiltration with lidocaine (2%), a small incision is made with a scalpel on the overlying skin. The needle is then advanced and the fascia traversed. Once in the muscle, the tip of the needle is advanced ≈3 cm and aspiration

applied through the back of the needle to enhance the amount of tissue protruding into the side-port cutting window. A sharp and quick cut is made and the specimen extracted. Usually more than 100 mg of wet-weight tissue is obtained. This tissue is dabbed dry, weighed, and cut into pieces that are immediately frozen in liquid nitrogen. The incision is closed with a simple steristrip; a pad dressing is applied at the end of the visit. Complications can include pain/soreness and superficial hematoma.

Adipose Biopsy Techniques: At the time of biopsy, ~ 1.0 gram of fat tissue will be extracted from just lateral to the umbilicus on the abdomen by aspiration under local anesthesia. We have successfully and safely used this technique to harvest samples in more than 100 patients to date participating in ongoing studies at our institution. Immediately after harvest, the sample is divided two ways by the lab technician. The first sample is placed in buffer and taken for size and insulin sensitivity measures. The second sample is then stored at -80° C for later analysis.

Biopsy Anticipated adverse events: Prior to the aspiration fat and muscle biopsies, a local anesthetic is injected into the skin. An allergic reaction to the anesthetic is rare (less than 1 in 10,000). Significant bleeding from the fat or muscle biopsy is rare. Baseline lab work will include measurement of platelets, INR and PTT to assure these levels are normal prior to the biopsies. Potential subjects taking regular medications that may have an anticoagulant affect will also be excluded from participation in the study. Infection of a fat biopsy may occur in up to 1 in 10 cases. A small scar will result at the biopsy site. The scar is usually smaller than the biopsy incision and is frequently almost invisible.

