Studies will be reviewed and approved by the OHSU Institutional Review Board (IRB). All subjects will be admitted to the inpatient unit of the Oregon Clinical and Translational Research Institute (OCTRI). Nursing staff and the investigative team will monitor subjects and care for wound or bleeding complications as a result of catheter placement and biopsy. To prevent radiation exposure to a fetus, a urine pregnancy test will be completed for females of child bearing potential prior to each DEXA Scan. Subjects who are pregnant will be excluded. A stable isotope $^2\text{H}_2$ glucose will be given to subjects. As noted above, the safety of stable isotopes is well documented and does not pose an added risk to the subjects (46). Special care will be taken to explain the use of stable isotopes to the subjects and their families. Plasma glucose will be monitored during the clamp procedure. The MD will discharge subjects at the end of each admission after a physical exam, vital signs are normal and they have no complaints of muscle pain. If they do have muscle pain, we will check a plasma creatine kinase (CK) level prior to discharge.

E. Confidentiality

Upon enrollment, subjects will be assigned a unique identifier that will be used instead of their name, medical record number or other personally identifying information. To ensure confidentiality, all data and specimens collected will be kept in locked laboratory facilities. Urine, blood, muscle and adipose samples will be stored with a unique identifier in locked laboratory facilities at OHSU. Long-term storage of blood muscle and adipose will be stored at -80°C and urine samples will be stored at -20 °C in the laboratory of [name]. The laboratory is a locked facility in the [name] at OHSU, Portland, Oregon. Only the PI and study staff will have access to paper records and the key code which will be stored in locked filing cabinets in restricted access offices at OHSU. Computer files of collected data will be password protected and stored on a restricted drive behind the OHSU firewall. The study coordinator will code urine, blood, muscle and adipose samples with the study ID code to remove any identifiable information on the sample prior to sending the samples to other laboratories for analysis. Subject's names or other identifiable information will not be published or shared with outside research facilities.

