F. Potential Benefits of the Proposed Research to the Subjects and Others

The proposed studies may provide new insights into the relationship between fatty acid oxidation and the development of insulin resistance in humans. This knowledge will be useful in designing future pharmaceutical targets for patients with insulin resistance and type 2 diabetes. The participants in this study will not benefit from the proposed research.

G. Data and Safety Monitoring Plan

1. Data quality and management. The principal investigators, [name], and [name], will review the data collection forms on an annual basis for completeness and accuracy of the data as well as

protocol compliance. A statement reflecting the results of the review will be sent to the NIH in the annual report (non-competing continuation). The data that will be reported to and monitored by the PI will include:

- Subject anthropometric data including height, weight and body composition
- Subject laboratory results
- Indirect calorimetry analysis of energy needs
- Data from the hyperinsulinemic-euglycemic clamp study
- Data from the magnetic resonance spectroscopy procedure
- Subject reports of adverse events or unanticipated problems

2. Adverse Event Definitions and Grading: An adverse event (AE) is defined as any unfavorable or unintended sign (including an abnormal laboratory finding), symptom or disease temporally associated with the use of a medical treatment or procedure that may or may not be considered related to the medical treatment or procedure. Adverse events in this study are evaluated for relationship to study intervention by a physician co-investigator using the Common Terminology Criteria for Adverse Events version 4.0. This grading criterion is listed as follows:

Grade 1: Mild; asymptomatic or mild symptoms; clinical or diagnostic observations only; intervention not indicated.

Grade 2: Moderate; minimal, local, or noninvasive intervention indicated; limiting age-appropriate instrumental activities of daily living.

Grade 3: Severe or medically significant but not immediately life-threatening; hospitalization indicated; disabling; limiting self-care activities of daily living.

Grade 4: Life-threatening consequences; urgent intervention needed.

Grade 5: Death related to AE.

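### CK is measured only if a subject reports muscle pain before discharge, so a triggered value has no pre-infusion value from the same patient to be read against

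*Combined protocol and SAP*

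**What the plan says.** Section VI.D (Protection Against Risk) makes discharge depend on a physical exam, normal vital signs and the absence of muscle pain. It then adds: "If they do have muscle pain, we will check a plasma creatine kinase (CK) level prior to discharge". This is the only place where CK is named.

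The scheduled blood work is listed elsewhere:

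- Section III, under anticipated adverse events of the biopsies: "Baseline lab work will include measurement of platelets, INR and PTT to assure these levels are normal prior to the biopsies".
- Table 4 has one general safety blood panel, "CBC with platelets, INR, PTT", at admission or on Day 1, plus a pregnancy test where applicable.
- Section III, clamp sampling: "Additional blood samples will be collected every 60 minutes for insulin, ketones, and FFA, and at the beginning and end of the clamp", the last two for labelled glucose and metabolomics.

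On the order of events, Section III keeps the infusions running through the biopsies, and only after "completion of the muscle and fat biopsies, the insulin and intralipid or glycerol/saline infusions will be stopped". Then: "Subjects will rest overnight and consume a standardized breakfast the following day (Day 3) and be discharged to home". On the muscle biopsy, the technique paragraph says: "Complications can include pain/soreness and superficial hematoma". Section VI.G.2 also lists biopsy discomfort among the expected risks.

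On attribution, Section VI.G.2 says: "Adverse events in this study are evaluated for relationship to study intervention by a physician co-investigator".

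**The concern.** The background to Specific Aim 1 names recurrent rhabdomyolysis as a feature of adult long-chain disease, chiefly after long fasts or exercise. The safety paragraph in Section III relies on the variable glucose infusion to avoid it during the lipid clamp. If a patient has muscle pain on Day 3, the physician orders a CK and must judge whether the event is related to the intervention. Two things make that judgement harder than it need be.

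First, there is no planned value from before the infusion. A raised CK could have been raised on arrival, and nothing in the plan would show it. Second, muscle pain is not specific in this protocol, because a muscle biopsy has been taken the day before and can cause soreness by itself.

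What is at stake is how well one safety result can be interpreted. No endpoint, estimate or planned comparison is affected.

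**Working it through.** No formula or stated figure is in question. The check is whether CK is scheduled anywhere, and what comes before a triggered value.

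**Where CK could appear**

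| Place | Content | CK? |
|---|---|---|
| Table 4, all days | Blood count with platelets, INR, PTT; pregnancy test | No |
| Pre-biopsy labs, Section III | Platelets, INR, PTT | No |
| Clamp samples, Section III | Glucose, insulin, ketones, FFA, labelled glucose, metabolomics | No |
| Assay list, Section IV | Insulin, leptin, adiponectin, FFA | No |
| Monitoring data, Section VI.G.1 | Laboratory results, not itemised | Not named |
| Discharge rule, Section VI.D | CK if muscle pain | Only if triggered |

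The assay list is weak evidence by itself, since it also omits ketones, which are sampled. The other rows do not depend on it.

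**Order of events at a planned admission**

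1. Admission or Day 1: blood count, INR, PTT, physical exam. No CK.
2. Day 2: clamp with intralipid or glycerol/saline. The muscle biopsy is taken near the end, with the infusion still running.
3. Day 3: discharge check. CK only on a complaint of muscle pain.

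A triggered CK therefore comes after both the infusion and the biopsy, with no planned value before either. The technique paragraph places the biopsy in the vastus lateralis. A sentence in the Aim 2 preliminary data mentions soleus. The order is the same for either muscle.

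**Size of the gap**

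- Long-chain patients (Section II): 8 CPT2 + 8 VLCAD + 8 LCHAD/TFP = 24.
- Planned admissions: 24 × 2 = 48, of which 24 are with intralipid and 24 with glycerol/saline.
- Scheduled CK values over those 48 admissions: 0.
- Planned admissions with a muscle biopsy: 2 of 2 per patient.

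**What the documents support about the biopsy**

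They say it can cause pain, soreness and haematoma. That is enough to show that the pain trigger is not specific. They do not say that it raises CK.

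**The case against.** The strongest case for the plan is that symptom-triggered testing is a defensible choice here. Section VI.A argues that decompensation occurs when glucose or energy is lacking, and that the dextrose infusion supplies the alternative fuel. The one case report of intravenous lipid that it cites had raised acylcarnitines but no adverse event. The background to Aim 1 calls these patients medically stable when glucose supply is adequate.

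The plan also has real safeguards: glucose monitoring during the clamp and for an hour after the insulin stops, a meal, an overnight stay, a physical exam at admission and another before discharge, real-time review of adverse events by a physician, and an Independent Safety Monitor. The admission exam and medical history give a clinical baseline. Nothing stops the discharging physician from repeating a CK, and stored blood might allow a later baseline assay.

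Most of this stands, and it keeps the point small. It does not supply a baseline CK. A clinical exam is not a CK value, and the plan makes no provision for assaying stored blood in time for a discharge decision.

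A reader might infer more than the documents support:

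- **The CK level is distorted by the biopsy.** This is an assumption. The documents support only an effect on the pain trigger.
- **Harmful rises without pain are being missed.** Such a rise would indeed go unmeasured, but the documents do not say how often it happens or whether it causes harm.
- **The amount of lipid infused shows a muscle hazard.** The documents link it to no CK or muscle outcome.

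**Conclusion.** The point holds as a cheap, low-priority improvement. CK is pain-triggered only, none is scheduled at any of the 48 planned long-chain admissions, a triggered value has no pre-infusion value from the same patient, and biopsy soreness can itself set off the trigger.

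This rests on reading Table 4 as applying to each admission, and on the planned 8 patients per diagnosis. It does not rest on any assumed rate of CK rise or on any effect of the biopsy on CK.

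It would be wrong to conclude that the plan is unsafe. The documents give no CK rate and no evidence of harm, and the safeguards are substantial. Nor do they support a routine testing schedule with a discharge cut-off. A sample at the end of the clamp may be too early to show a rise (CK timing is not in the documents). A routine Day 3 sample would follow the biopsy and might delay discharge for patients who have travelled far. Section VI.G.2 gives only generic severity grades, with no CK limits from which to set a cut-off.

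**What to change.** For CPT2, VLCAD and LCHAD/TFP patients, add CK to the existing blood draw at admission or Day 1 (the blood count, INR and PTT row of Table 4) at both admissions. In Section VI.D, state that a pain-triggered CK is read against that baseline. Keep the pain trigger as it is.

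MCAD patients can be left out, because the background to Aim 1 says that recurrent rhabdomyolysis is not observed in those adults.

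Cost: 24 × 2 = 48 routine assays on blood already being drawn, with no new venipuncture. Repeat visits would add one assay each. The compensation section allows up to two per subject, so the extreme upper limit is a further 24 × 2 = 48, though in practice only a few are likely. The downside is an occasional raised baseline that needs clinical review before the clamp goes ahead.

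An end-of-clamp CK, a routine Day 3 CK and a grade-based discharge rule are optional extras for the investigators to weigh. They are not part of this recommendation.
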